The DLT observation period is the first 2 cycles (approximately 28 days). A DLT-evaluable participant must have completed 2 cycles of treatment or have been discontinued from study treatment because of a DLT; DLT nonevaluable participants will be replaced.

Part 2:

In Part 2 of the study, the recommended dose confirmed in Part 1 will be evaluated for activity in 26 additional participants. Refer to [Section 1.1](#) for an overview of study design, and [Section 6](#) for details of administration of study intervention.

The expected duration of study intervention for participants may vary, based on the disease progression date; the median expected duration of the study per participant is estimated as 34 weeks (up to 4 weeks for screening, a median of 18 weeks for treatment, and a median of 12 weeks for end-of-treatment assessments and the safety follow-up visit).

Serious adverse events/AESIs (regardless of relationship with study treatment) and IMP-related AEs ongoing at the end of study treatment, and any new IMP-related AEs/SAEs/AESIs will be followed until resolution or stabilization (defined as an event ongoing without any change for at least 3 months). A safety follow-up visit will be performed 90 days after the last IMP administration. If all ongoing IMP related AEs/SAEs/AESIs are resolved or stabilized, no further safety follow-up visit will be needed; otherwise, an on-site follow-up visit will be performed every 12 weeks.

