- E 25. Washout period before the first administration of study intervention of less than 3 weeks or less than 5 times the half-life, whichever is shorter, for prior antitumor therapy (chemotherapy, targeted agents, immunotherapy and radiotherapy, or any investigational treatment).

- E 26. Poor coagulation as defined by International Normalized Ratio (INR) ≥ 1.5 or prothrombin time (PT) $\geq 1.5 \times$ upper limit of normal (ULN) and partial thromboplastin time/activated partial thromboplastin time (PTT/aPTT) $\geq 1.5 \times$ ULN, unless the participant is receiving anticoagulation therapy. Participants receiving warfarin must be switched to low-molecular-weight heparin and must achieve a stable coagulation profile prior to the first IMP administration.

Prior/concurrent clinical study experience

- E 27. Previous enrollment in this study, current participation in any other clinical study involving an investigational study treatment, or any other type of medical research.

Diagnostic assessments

- E 28. Poor organ function as defined by any one of the following prior to IMP administration:
- a) Serum creatinine $>1.5 \times$ ULN or estimated glomerular filtration rate (eGFR) <60 mL/min/1.73 m² as estimated using a Modification of Diet in Renal Disease (MDRD) formula.
 - b) Total bilirubin $>1.0 \times$ ULN (excluding congenital conjugation disorders [Gilberts], for whom total bilirubin $\leq 3.0 \times$ ULN, with direct bilirubin $\leq 1.5 \times$ ULN, is allowed).
or
aspartate aminotransferase (AST), alanine aminotransferase (ALT) $>2.5 \times$ ULN (In case of documented liver metastasis, AST, ALT $<5 \times$ ULN is allowed).
 - c) Neutrophils $<1.5 \times 10^9$ /L, platelet count $<100 \times 10^9$ /L, or hemoglobin <9 g/dL (blood infusion-free for at least 2 weeks).
- E 29. Urine dipstick or routine analysis indicating proteinuria of 2+ or higher, unless a 24 hour urine collection demonstrates <1000 mg of protein.

Other exclusions

- E 30. Accommodation in an institution because of regulatory or legal order (eg, prisoners or participants who are legally institutionalized).
- E 31. Any country-related specific regulation that would prevent the participant from entering the study - see Appendix 8 ([Section 10.8](#)) of the protocol (country-specific requirements).

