Administration of the study treatment will be discontinued in the event of a TEAE that persists despite appropriate dose modifications or any other AE that, in the opinion of the Investigator, warrants discontinuation.

Ramucirumab or tusamitamab ravtansine can be discontinued prematurely. The patient will remain on study treatment until the last IMP can be discontinued for disease progression, unacceptable AE, or the participant's or investigator's decision to stop the treatment. The reason for premature discontinuation will be captured in the appropriate eCRF page.

Dose modifications different from those stated in the protocol should be made only in consultation with the Sponsor unless required for immediate participant safety.

All changes to study treatment administration must be recorded in the eCRF.

In the event of neutropenia or febrile neutropenia, therapeutic G-CSF should be administered according to the current American Society of Clinical Oncology (ASCO) guidelines ([13](#)); for specific recommendations for this study, refer to Appendix 6 ([Section 10.6](#)).

The acceptable treatment window for tusamitamab ravtansine and ramucirumab administration is ± 2 days.

See Appendix 6 in [Section 10.6](#) for further guidance for dose modification or discontinuation. Approved product labels for ramucirumab should be followed for supportive care and dose modification requirement due AEs not listed in [Section 10.6](#). During the conduct of the study, a second dose reduction may be needed; such an action must be decided in a case-by-case discussion with the Sponsor. In case a dose reduction is necessary for Cycle 2 and subsequent cycles, the study intervention will be administered as follows in [Table 7](#).

Table 7 - Dose modification for toxicity

Drug name	Dose	1 st dose reduction ^a	2 nd dose reduction ^a
tusamitamab ravtansine	100 mg/m ² Q2W	80 mg/m ² Q2W	(not permitted)
ramucirumab	8 mg/kg Q2W	6 mg/kg Q2W	5 mg/kg Q2W

^a Dose modification is applicable from Cycle 2. At Cycle 1 the dose will remain the recommended dose (170 mg/m² or 150 mg/m²).

Any participant who requires a tusamitamab ravtansine or ramucirumab dose reduction will continue to receive a reduced dose until discontinuation from tusamitamab ravtansine/ramucirumab or discontinuation from the study.

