Any patient who has had 1 tusamitamab ravtansine dose reduction or 2 ramucirumab dose reductions and who experiences an event that would cause an additional dose reduction must be discontinued from tusamitamab ravtansine/ramucirumab.

If 1 of the 2 drugs (tusamitamab ravtansine or ramucirumab) is prematurely permanently discontinued, the other drug can be continued until disease progression.

Retreatment of a patient requiring a dose delay of more than 1 month will need to be justified by an individual case risk-benefit assessment.

6.5.1 Retreatment criteria: Part 1 and Part 2

All participants entered into the study will be treated at Day 1. A participant may receive additional study interventions if he/she meets retreatment criteria as determined by the Investigator and agrees to be retreated.

At Day 1, the participant must meet all of the following criteria to be eligible for retreatment:

- Neutrophil count $\geq 1.5 \times 10^9/L$.
- Platelets $\geq 100 \times 10^9/L$.
- Total bilirubin $\leq 1.5 \times ULN$.
- AST, ALT $\leq 2.5 \times ULN$ or $\leq 5 \times ULN$ in case of documented liver metastasis.
- No IMP-related toxicity Grade >1 (except for alopecia) or baseline severity.

- Urine protein:
 - <2+ on dipstick or urinalysis for C1D1
 - ≤2+ on dipstick or urinalysis for subsequent infusions
- OR
- <2 g on 24 hour urine collection.
- Hypertension is controlled. Every attempt should be made to control blood pressure (<150 mmHg systolic and <90 mmHg diastolic).
 - Wound healing: any wound is fully healed.

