9.2 POPULATIONS FOR ANALYSES

The following populations for analyses are defined in [Table 9](#):

Table 9 - Populations for analyses

Population	Description
Prescreened	All participants who signed the prescreening informed consent for CEACAM5 assessment of their biopsy.
Screened	All participants who signed screening informed consent for study participation.
Enrolled	Participants from screened population who have been allocated to intervention regardless of whether the intervention was received or not.
All-treated	All enrolled participants exposed to the study treatment, regardless of the amount of treatment administered. This population is the primary population for all efficacy parameters.
DLT-Evaluable (Part1)	All enrolled participants who received 2 cycles with at least 80% of the intended dose for both tusamitamab ravtansine and ramucirumab at each of the first 2 infusions unless they discontinued the study intervention before the end of Cycle 2 due to a DLT.
Activity	All treated participants who have measurable disease at study entry and at least 1 postbaseline evaluable tumor assessment. Participants with no postbaseline evaluable tumor assessment but with an early clinical progression or who died from disease progression will also be included in this set. This population is the secondary population for all efficacy parameters.
PK	All participants from the all-treated population with at least 1 postbaseline PK concentration (whatever the cycle and even if dosing is incomplete) with adequate documentation of dosing and sampling dates and times.
ATA	All participants from the all-treated population with at least 1 postbaseline ATA result (negative, positive or inconclusive).

Abbreviations: ATA = antitherapeutic antibody; CEACAM5 = carcinoembryonic antigen-related cell adhesion molecule 5; DLT = dose-limiting toxicity; PK = pharmacokinetic.

Participants exposed to study intervention before or without being enrolled will not be considered enrolled and will not be included in any analysis population. The safety experience of these participants will be reported separately.

Enrolled participants for whom it is unclear whether they took the study intervention will be considered as exposed and will be included in the safety population.

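### Gilbert-type participants may enter with total bilirubin up to 3.0 x ULN, but the retreatment rule stops at 1.5 x ULN with no exception, so some get the loading dose and, as written, no Cycle 2

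*Protocol*

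**What the plan says.** Protocol 5.2, E28 b), excludes anyone with total bilirubin above 1.0 x ULN, with one carve-out: "excluding congenital conjugation disorders [Gilberts], for whom total bilirubin" is allowed up to 3.0 x ULN, provided direct bilirubin is at most 1.5 x ULN. The same item relaxes the AST/ALT limit from 2.5 to below 5 x ULN for participants with liver metastases.

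Protocol 6.5.1 opens with "All participants entered into the study will be treated at Day 1". It continues: "At Day 1, the participant must meet all of the following criteria to be eligible for retreatment". The list that follows includes total bilirubin of at most 1.5 x ULN, without qualification. The next bullet, on AST/ALT, does carry its entry exception over: up to 5 x ULN "in case of documented liver metastasis".

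For Part 1, the DLT-evaluable population in Protocol 9.2 is "All enrolled participants who received 2 cycles with at least 80% of the intended dose" of both drugs, unless treatment stopped early because of a DLT. Protocol 4.1 adds that "DLT nonevaluable participants will be replaced".

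**The concern.** The entry criteria deliberately admit people whose bilirubin is raised for a constitutional reason. The retreatment criteria then treat the same value as a reason to withhold the drug. Someone with a stable 2.0 x ULN, for example, is eligible, receives 170 mg/m² (or 150 mg/m²) of tusamitamab ravtansine with ramucirumab, and fails the Cycle 2 check on a number that has not changed and is not drug-related.

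Three things are at stake. The participant takes on the risk of the highest dose in the regimen and then loses continued treatment. Part 1 loses a DLT-evaluable participant and must find a replacement. The response analysis keeps a participant whose exposure was cut short for a reason unrelated to tolerability or activity. Sites may also resolve the clash differently, by holding, by deviating or by asking the Sponsor.

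**Working it through.** The plan gives no figure to reproduce here. The check has three steps.

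**1. Compare each laboratory limit that appears both at entry and at retreatment.**

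| Parameter | Entry (E28, E29) | Retreatment (6.5.1) | Retreatment is |
|---|---|---|---|
| Neutrophils | at least 1.5 x 10⁹/L | at least 1.5 x 10⁹/L | equal |
| Platelets | at least 100 x 10⁹/L | at least 100 x 10⁹/L | equal |
| AST/ALT | up to 2.5 x ULN | up to 2.5 x ULN | equal |
| AST/ALT, liver metastases | below 5 x ULN | up to 5 x ULN | equal in effect |
| 24 h urine protein | below 1000 mg | below 2 g | looser |
| Total bilirubin, no Gilbert | up to 1.0 x ULN | up to 1.5 x ULN | looser |
| Total bilirubin, Gilbert | up to 3.0 x ULN, direct up to 1.5 x ULN | up to 1.5 x ULN | **stricter** |

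Only the Gilbert row tightens after the first dose. E28 b) raises the entry limit for this group by 3.0 − 1.0 = 2.0 x ULN, and the top 3.0 − 1.5 = 1.5 x ULN of that range fails 6.5.1. These are widths of a range, not shares of participants.

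**2. Look for the missing exception elsewhere.**

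- The baseline-severity wording in 6.5.1 sits in a separate bullet on IMP-related toxicity. A Gilbert baseline is not IMP-related.
- 6.5.1 leaves it to the Investigator to judge whether the criteria are met. It gives no power to waive one, and Protocol 8 rules out waivers and exemptions.
- Protocol 8.2.7.5 (liver function tests) has no Gilbert provision, and Appendix 6 has no bilirubin or liver row.
- E32 lets the Investigator exclude an unsuitable participant, but using it here would cancel the allowance in E28 b).

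**3. Size the consequence per affected participant.** The documents give no prevalence, and none is assumed.

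- Part 1 replacement, on top of 6 to 12 DLT-evaluable participants: 1/6 = 16.7% to 1/12 = 8.3% more, each with its own DLT window of about 28 days.
- Weight in the response rate, using the planned 32: 1/32 = 3.1%.
- Extreme case, assuming a true response rate of 20% to 30% (not in the documents) and no chance of response after a single infusion: 0.20/32 = 0.6 points to 0.30/32 = 0.9 points off the expected response rate.

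A Part 1 participant treated at the recommended dose counts under both headings: replaced for the DLT assessment and kept in the response denominator.

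**The case against.** The strongest objection is about size. Few participants can be affected, and the study tests no hypothesis. A Clopper-Pearson 95% interval for 8 responders in 32 runs from 11.5% to 43.4%, so a shift below one point is lost in the imprecision. The extreme case is also harsh: Protocol 9.3.2.2 assesses response regardless of discontinuation, and Protocol 4.3 describes shrinkage in participants who had only two infusions at 120 mg/m² before a delay and reduction. This stands, and the point should not be presented as a bias in the response rate. The figure of 32 is the target number evaluable for activity; the primary denominator is all treated participants at the recommended dose, which may be larger, so 3.1% is approximate.

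Second, one bullet in 6.5.1 sets a urine-protein limit for C1D1, so the list could be read as governing the first dose too. The sentence that everyone entered is treated at Day 1 points the other way. On the alternative reading the participant is never dosed, and the conflict with E28 b) simply comes earlier.

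Third, the rule imposes a hold, not a permanent stop, and a participant whose value falls to 1.5 x ULN can resume. That is correct, and the concern is limited to a baseline that stays above it.

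Fourth, Protocol 6.5 provides that "Dose modifications different from those stated in the protocol should be made only in consultation with the Sponsor". That covers dose changes rather than retreatment criteria, and even on a generous reading it is a case-by-case workaround.

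**Conclusion.** The concern holds. The two rules conflict for participants with a congenital conjugation disorder whose total bilirubin stays above 1.5 and up to 3.0 x ULN, and no other section resolves it. The liver-metastasis exception was carried into 6.5.1 and this one was not, which suggests an oversight rather than a policy.

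The effect on the response estimate is small: about 3.1% of the denominator per affected participant, and at most 0.6 to 0.9 points under the assumed response rates and the extreme case above. In Part 1 the cost is one replacement per affected participant. The conclusion rests on the thresholds as written, a stable baseline, and the reading that the first dose is given to everyone entered. The change is worth making so that participants are not given a loading dose and then held for an unchanged baseline value, and so that all sites follow one dosing rule.

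**What to change.** Amend the bilirubin bullet in Protocol 6.5.1 to read:

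> Total bilirubin ≤1.5 x ULN (for congenital conjugation disorders [Gilbert]: total bilirubin ≤3.0 x ULN with direct bilirubin ≤1.5 x ULN).

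This repeats a level the sponsor already accepts for the first dose. The direct-bilirubin cap and the AST/ALT limits would still hold dosing for new liver injury. An allowance tied to each participant's own baseline would be narrower, but is not needed for consistency with E28 b). If the sponsor does not want anyone dosed above 1.5 x ULN, the alternative is to lower the E28 b) allowance to 1.5 x ULN. One of the two sections has to change.

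The cost is a minor protocol amendment with IRB/IEC approval and, if it is classed as substantial, health-authority approval (Protocol 10.1.1). It adds no participants and no tests: conjugated bilirubin is already in the required chemistry panel (Appendix 2, Table 10), and the schedule of activities has liver function tests before each cycle and weekly during the first two.

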5.3 LIFESTYLE CONSIDERATIONS

Not applicable.

5.4 SCREEN FAILURES

Screen failures are defined as participants who consent to participate in the clinical study but are not subsequently enrolled. A minimal set of screen failure information is required to ensure transparent reporting of screen failure participants to meet the Consolidated Standards of Reporting Trials (CONSORT) publishing requirements and to respond to queries from regulatory authorities. Minimal information includes demography, screen failure reasons, eligibility criteria, and any SAE.

For individuals who do not meet the criteria for participation in this study (screen failure) and for whom resolution of the screen failure may not be expected within a reasonable time frame, the screen failure will be recorded.

Individuals who do not meet the criteria for participation in this study (screen failure) may be rescreened. Rescreened participants should be assigned a participant number different from that for the initial screening, and all the screening procedures will be repeated and entered in the screening visit pages.

In case the participant is a temporary screen failure, there is no need to have participant reconsent (ie, new ICF signed) if the participant finally participates in the trial. However, if the reason for the temporary screen failure might have altered the participant's initial given agreement to participate, the Investigator should ask the participant and confirm the participant's willingness to continue or redo some screening procedures and participate in the trial. This oral agreement should be documented in the participant's chart. All the tests outside protocol-specified window should be repeated and entered to the additional pages.

5.5 CRITERIA FOR TEMPORARILY DELAYING ENROLLMENT

During a regional or national emergency declared by a governmental agency, the Investigator/site should assess the site's capacity to conduct procedures for a new participant to be enrolled into the study before initiating any screening procedures. Site capacity also should be ensured before enrollment of a participant. If the site is unable to adequately follow protocol mandated procedures, contingency measures proposed in Appendix 9 ([Section 10.9](#)) should be applicable to prescreening/screening/enrollment/administration of study treatment.

6 STUDY INTERVENTIONS AND CONCOMITANT THERAPY

Study intervention is defined as any investigational interventions, marketed products, placebo, or medical devices intended to be administered to a study participant according to the study protocol. Treatment preparation and administration (including compatible materials), handling, storage and accountability will be further detailed in the Pharmacy Manual.

6.1 STUDY INTERVENTIONS ADMINISTERED

Table 4 - Overview of study interventions administered

Intervention label	Tusamitamab ravtansine	Ramucirumab
Intervention name	tusamitamab ravtansine	ramucirumab
Type	Drug	Drug
Dose formulation	concentrated solution for IV	concentrated solution for IV
Unit dose strength(s)	5 mg/mL	10 mg/mL
Dosage levels^a	170 (150) mg/m ² Cycle 1 then 100 mg/m ² Q2W	8 mg/kg Q2W
Route of administration	IV infusion	IV infusion
Use	experimental	experimental
IMP or NIMP	IMP	IMP
Packaging and labeling	Supplied in a 30 mL glass vial with a white plastic flip-off cap, containing 125 mg/25 mL tusamitamab ravtansine, and labelled with a multilingual booklet	Supplied in a single-dose vial (100 mg/10 mL or 500 mg/50 mL), labeled with a multilingual booklet, and individually packaged in a carton
Current/Former names or aliases	tusamitamab ravtansine/SAR408701	Cyramza®

Abbreviations: DL -1 = dose level -1; IMP = investigational medicinal product; IV = intravenous; NIMP = noninvestigational medicinal product; Q2W = every 2 weeks.

^a The tusamitamab ravtansine starting dose is 170 mg/m²; the dose may be decreased to 150 mg/m² (DL -1)

Table 5 - Single arm interventions

Arm name	Tusamitamab ravtansine/ramucirumab (single arm)
Associated interventions	tusamitamab ravtansine, ramucirumab

For a regional or national emergency declared by a governmental agency that results in travel restrictions, confinement, or restricted site access, contingency measures are included in Appendix 9: Contingency Measures for a regional or national emergency that is declared by a governmental agency ([Section 10.9](#)).

Study medication infusion:

Infusion via a central line is preferred, if available. Prior to dosing, each participant's dose will be individually prepared by the study pharmacist and labeled with protocol number, participant number, and treatment description.

On Day 1 of each treatment cycle, the patient's BSA will be determined using the most recent weight available on the day of the infusion preparation: the weight on the day of the infusion or the most recent weight, assuming it was assessed in a reasonable time frame according to Investigator assessment. If the infusion is prepared with the most recent weight assessed in a reasonable time frame, this will not prevent assessment of weight on D1 of each cycle, which must be recorded in the eCRF. The dose needs to be adjusted if change in body weight is >5% of weight at the previous cycle.

Investigational medicinal products:

Ramucirumab: Ramucirumab should be administered prior to tusamitamab ravtansine infusion. Using a controlled infusion pump, ramucirumab will be administered by IV infusion over 1 hour on Day 1 of each cycle. If the first infusion is tolerated, all subsequent ramucirumab infusions may be administered over 30 minutes. In case of IRR, Grade 1 or 2, the infusion rate of ramucirumab will be reduced by 50%.

Tusamitamab ravtansine: Infusion of tusamitamab ravtansine should be initiated after the end of ramucirumab infusion. As IRRs may occur during or following ramucirumab administration, a 1 hour observation period following the ramucirumab infusion is mandatory prior the initiation of tusamitamab ravtansine administration for the first 2 infusions. If the patient shows no evidence of an IRR with the first 2 infusions of ramucirumab, no observation period is required for subsequent infusions. In the event an IRR occurs thereafter, the 1 hour observation should be reinstated.

Using a controlled infusion pump, tusamitamab ravtansine will be administered by IV infusion over 1 hour 30 minutes. For a participant with a BSA >2.2 m², the calculated dose of tusamitamab ravtansine will be based on a BSA of 2.2 m². After the first administration of tusamitamab ravtansine, participants should be observed for acute reactions on site for up to 4 hours depending on any sign of IRR. In case of a Grade 1-2 IRR, tusamitamab ravtansine must be interrupted and may be resumed only after patient recovery, at half of the previous infusion rate, with a minimum authorized flow rate at 33 mL/h. Detailed instructions for dilution and administration of the IMP is provided in Pharmacy Manual.

Noninvestigational medicinal products:

Premedication:

Both tusamitamab ravtansine and ramucirumab have potential risk of IRR; thus, premedication with an IV histamine-1 receptor antagonist (diphenhydramine 50 mg IV or equivalent; eg, cetirizine, promethazine, dexchlorpheniramine, according to local approval and availability) will be given approximately at least 15 minutes before ramucirumab administration. If a participant previously experienced an IRR following a dose of ramucirumab or tusamitamab

ravtansine, premedication will also include corticosteroids equivalent to 10 mg IV dexamethasone, and acetaminophen/paracetamol for future infusions. All drugs used as premedication will be entered on the concomitant premedication page.

